#### Primary analysis:

The primary analysis will be a direct comparison of the mortality rate of ovarian cancer:

- between the control arm and multimodal arm
- between the control arm and ultrasound arm.

Events of interest will be those deaths signed off by Outcome Review as primarily caused by ovarian cancer (ICD-10: C56) or tubal cancer (C57.0) or undesignated ovarian/tubal/peritoneal cancer. The analysis will be based on 'intention to treat', so that no allowances for non-compliance to screening will be made. Similarly for any 'contamination' that occurs. A Cox regression model will be used to model the difference in mortality rate between the control arm and each individual screen arm. Several sensitivity analyses will be performed to validate the primary outcome result.

**Secondary analyses:** This will include assessing the performance characteristics of the screening modalities, namely their sensitivity, specificity and positive predictive value, compliance with screening and complication rates resulting from trial surgery using the conventional ratios with appropriate confidence intervals.

There will be an interim analysis performed at the point where half the expected number of control group deaths due to OC (111) is reached. This will include all primary and secondary endpoints detailed above as well as intermediate endpoints for OC mortality such as stage of OC and lead time (mean duration of preclinical disease) estimated from the ratio of prevalence (at the first screen) and incidence (annual) rates of OC.

The economic analysis will be undertaken on the calculated cost-effectiveness ratios that are crucial to the trial. It will include both a within trial analysis and a modeling analysis. The within trial analysis will consider the cost-effectiveness ratios relating to protocol driven resource use. The modeling analysis will take into account standard practice which would reflect the implementation of a National Screening Programme (as this may differ

from study protocol resource utilisation), and extrapolation of trial results over a longer time frame to include lifetime benefits.

Exploratory analysis: With women followed for up to 13 years in the first instance until 2014 and during extended follow-up until 2024 there is great scope to produce an extensive array of exploratory analyses. Characteristics of the randomised population will be compiled using standard descriptive statistics of the (baseline) recruitment data. In addition, the use of postcodes can provide relevant deprivation indices. These will be further enhanced by data obtained via from postal questionnaires. The collection from HSCIC of incidence data of all other cancer types and mortality data of all causes allows investigation of numerous potential links between incidence and mortality and the population characteristics.

The vast amount of data generated from the screens themselves, pertaining to ultrasounds, blood tests, surgery outcomes and histopathology results will be analysed as 1) a quality control of the screens (e.g. percentage of ovaries 'seen' by ultrasound sonographers) 2) as worthwhile scientific data in its own right (e.g. average ovarian volume) and 3) as further possible explanatory variables in studies on other cause mortality and incidence.

**Predefined subgroups**: The benefit of screening, and in particular the positive predictive value (PPV), will depend on the absolute level of risk for the population. Women at a particularly high risk of developing OC due to familial predisposition are excluded from this trial. Apart from differences between age groups, long-term use of oral contraceptive pills

and number of pregnancies are known to be factors influencing the risk of developing OC.

The major subgroups to be explored and contrasted will be those defined as being 'low

risk' and 'intermediate risk' groups within this population. The 'low risk' group will be

defined as women with >3 full-term pregnancies or >5 years use of oral contraceptives;

the 'intermediate risk' group will be those women with <3 full-term pregnancies and <5

years use of oral contraceptives.

Start date: April 2001

End of screening date: 31st December 2011

Censorship for primary mortality analysis: 31st December 2014

Reporting date for above: June 2015

End of follow-up: December 2024

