11. Ethnic group, please place an "X" in the appropriate box. (If you are descended from more than one ethnic or racial group, please sellect the group you consider you belong to or choose "Any other ethnic origin")
White Indian Pakistani Chinese Bangladeshi
Black-African Black-Caribbean Black-other Any other ethnic origin
12. At what age did you first have your period?
13. How many pregnancies have you had which ended before they reached 6 months (including miscarriages, ectopic pregnancies)?
14. How many pregnancies have you had which lasted beyond 6 months (including all deliveries - both term and preterm)?
15. Have you ever taken the oral contraceptive pill?  If yes, how many years in total did you take the pill?  Yes No Years
16. Have you ever had a hysterectomy (removal of the womb)?  Yes No
17. Have you had a sterilisation operation (To block your tubes)?  Yes No
18. Have you ever had any treatment for infertility?

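### The predefined low-risk and intermediate-risk subgroups are not complementary: some women with exactly 3 pregnancies or exactly 5 pill years belong to neither

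*Protocol*

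**What the plan says.** The definitions are in the protocol's Statistical analysis plan section, in the paragraph headed Predefined subgroups, directly after the exploratory analyses. The paragraph argues that the benefit of screening, and the positive predictive value in particular, depends on absolute risk. It names pill use and number of pregnancies as risk factors, and calls the two resulting groups the major ones to be contrasted.

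- Low risk: "defined as women with >3 full-term pregnancies or >5 years use of oral contraceptives".
- Intermediate risk: "the 'intermediate risk' group will be those women with <3 full-term pregnancies and <5" years on the pill.

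Neither this paragraph nor any other gives a third category or a rule for the boundary values.

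The data come from the recruitment questionnaire. Item 13 asks "How many pregnancies have you had which ended before they reached 6 months". Item 14 asks "How many pregnancies have you had which lasted beyond 6 months (including all deliveries - both term and preterm". Item 15 asks about the pill: "If yes, how many years in total did you take the pill". The two follow-up questionnaires reproduced in the appendices contain no pregnancy count.

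**The concern.** Two groups meant to be contrasted within one trial population would normally divide it between them. Here the value 3 satisfies neither pregnancy condition and the value 5 satisfies neither pill condition. Three is an ordinary number of pregnancies, and five is a natural answer to a question about years.

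Followed as written, the rule removes these women from the contrast, so deaths in the two groups will not add up to the trial total. If the analyst instead assigns the women to a group, the protocol gives no guidance on which. Predefining subgroups is meant to remove that kind of choice.

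The second issue is the variable itself. The definitions rest on full-term pregnancies, and no form in the protocol separates term from preterm deliveries.

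**Working it through.** There is no planned figure to reproduce. The check is whether the two rules cover every case, followed by an illustration of size.

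**1. Coverage.** Write p for pregnancies and y for pill years.

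- Low risk: p > 3 or y > 5.
- Intermediate risk: p < 3 and y < 5.
- Not low risk means p ≤ 3 and y ≤ 5. Removing the intermediate group leaves p = 3 with y ≤ 5, and y = 5 with p ≤ 3.

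Applying both rules to every whole-number pair with p from 0 to 8 and y from 0 to 15:

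| Result | Pairs |
|---|---|
| In neither group | 9: p = 3 with y = 0 to 5 (6 pairs); p = 0 to 2 with y = 5 (3 pairs) |
| In both groups | 0 |

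Because low risk is joined by *or*, a woman with p = 3 and y > 5 is low risk, and so is one with y = 5 and p > 3. The gap is therefore smaller than all women on a boundary.

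**2. Repairs.** Each of these gives 0 unclassified pairs and 0 overlaps on the same grid:

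- (a) low: p ≥ 3 or y ≥ 5; intermediate: p < 3 and y < 5.
- (b) low: p > 3 or y > 5; intermediate: p ≤ 3 and y ≤ 5.

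Under (a) all nine pairs become low risk; under (b) all nine become intermediate risk. The choice moves the whole block of women from one group to the other.

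**3. Size (assumed inputs).** The protocol gives the number randomised, 202,638, and no distribution of p or y. Let a = P(p = 3), b = P(p > 3), c = P(y = 5), d = P(y > 5), with parity and pill use independent. Then

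unclassified share = a(1 − d) + c(1 − a − b).

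| a | b | c | d | a(1 − d) | c(1 − a − b) | Share | Women |
|---|---|---|---|---|---|---|---|
| 0.15 | 0.10 | 0.03 | 0.25 | 0.1125 | 0.0225 | 0.135 | 27,356 |
| 0.20 | 0.12 | 0.05 | 0.30 | 0.1400 | 0.0340 | 0.174 | 35,259 |
| 0.25 | 0.15 | 0.08 | 0.35 | 0.1625 | 0.0480 | 0.2105 | 42,655 |

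A second set of assumptions takes 12 to 25% with exactly 3 pregnancies, 70% of them with at most 5 pill years, and 65% with fewer than 3 pregnancies, 4% of whom report exactly 5 years. The share is then 0.12 × 0.70 + 0.65 × 0.04 = 0.084 + 0.026 = 0.110 at the low end, and 0.25 × 0.70 + 0.026 = 0.175 + 0.026 = 0.201 at the high end.

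Across both sets the share is about 11 to 21%. Most of it comes from the parity term. That matters because whole-number pill years are only inferred from the wording of item 15; if fractions were recorded, the second term would shrink and the first would remain.

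**4. The pregnancy variable.** Item 13 counts pregnancies ending before 6 months and item 14 counts all later ones, term and preterm together. Full-term pregnancies cannot be recovered from either item or from their difference.

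**The case against.** The strongest objection is that this is notation. A greater-or-equal sign may have been flattened when the PDF was read, and the protocol is loose with strict signs elsewhere: simple cysts are given as below or above 60 cm³ with nothing said about 60 itself. A lost sign cannot be ruled out. However, the greater-or-equal sign survives in the risk thresholds of the multimodal screening strategy, and the subgroup text as it stands is strict on both sides. Loose drafting would explain the gap without showing which side was meant.

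A second objection is that contrasting two separated groups and omitting a middle band is a legitimate design, and the protocol never says that the groups are exhaustive. That is true in principle. But no middle group is named, and the omitted set is not a clean band: a woman with 3 pregnancies is left out or classed as low risk depending on her pill use.

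A third is that a separate analysis plan may fix the cuts. It may, and the protocol does not say that the choice would be made after the data are seen. Still, the protocol states the cut-points itself, so this is a rule stated with a gap rather than a detail left for later.

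On the pregnancy variable the objection largely succeeds. Item 14 is a close proxy, and it was answered before randomisation, so any misclassification cannot depend on arm.

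**Conclusion.** The two definitions leave a gap, and this follows from the text alone. Women with exactly 3 pregnancies and at most 5 pill years, or exactly 5 pill years and at most 3 pregnancies, are in neither group. Their share is unknown; about 11 to 21% is an illustration that rests wholly on assumed distributions. The full-term wording is a minor mismatch. The definition should be corrected, but the consequence is limited to an exploratory contrast.

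A reader might infer more than the protocol supports:

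- That every woman on a boundary is lost. The *or* in the low-risk rule keeps some of them.
- That the main result is affected. The primary comparison, its intention-to-treat population and its power do not use these groups.
- That this is the only subgroup analysis planned. The protocol calls these the major subgroups, which leaves room for others, and it mentions age differences in the same paragraph.
- That the unclassified women carry a matching share of ovarian cancer deaths. The protocol itself treats parity and pill use as risk factors, so the share of deaths may differ.

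**What to change.** Rewrite the definition so that one side of each cut is inclusive, by either of these:

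- low risk is 3 or more pregnancies or 5 or more pill years, and intermediate risk is all other women; or
- low risk is more than 3 pregnancies or more than 5 pill years, and intermediate risk is at most 3 pregnancies and at most 5 pill years.

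The protocol does not show which was intended. The sponsor should choose and record the choice before any look at outcomes by arm, since it moves the whole unclassified block. If a separate analysis plan already fixes the cuts, the protocol should be aligned with it.

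In the same sentence, replace full-term pregnancies by the count defined in item 14 of the recruitment questionnaire. The cost is one sentence; all the data needed were collected at recruitment.

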**Publication policy** 

The credit for results addressing the core hypotheses of this collaborative effort lies with all

the members of the UKCTOCS team and authorship will include all names if investigators,

researchers at the coordinating centre and trial centre leads where possible. If the journal

does not permit this due to the number of authors, then the paper will be published under

the acronym - UKCTOCS group. The data and samples available offers numerous

opportunities for secondary studies which will be performed either by members of the

UKCTOCS team or in collaboration with other investigators. Authorship credit will be

based on the usual criteria. The entire UKCTOCS group will be acknowledged on all such

publications.

41

### **Funding**

The main trial is core funded by the Medical Research Council, Cancer Research UK and the Department of Health with additional support from Eve Appeal, Special Trustees Barts and the London and Special Trustees University College London Hospital. The Psychosocial Study is funded by the Medical Research Council.

## UK COLLABORATIVE TRIAL OF OVARIAN CANCER SCREENING (UKCTOCS)

Funding bodies	MRC, NHS R&D, CRC, ICRF, Gynaecology Cancer Research Fund (GCRF)
Design/Intervention	Randomised controlled trial with three arms:
	(1) A control group (no screening).
	(2) A multimodal group (annual screening with serum CA 125 as the primary test and
	CA125 and ultrasound as the secondary test).
	(3) An ultrasound group (annual screening with ultrasound as the primary test and repeat
	ultrasound in 6-8 weeks as the secondary test).
Objectives/aims:	Objective 1
	To establish the impact of screening on ovarian cancer mortality
	Objective 2
	To determine the physical morbidity of ovarian cancer screening.
	To determine the resource implications of screening.
	To record the psychological consequences of screening.
	To assess the feasibility of population screening for ovarian cancer as reflected by
	uptake of invitations and compliance rates with annual screening.
	To compare the performance of two screening strategies for ovarian cancer
	Objective 3
	To establish a serum bank for future assessment of novel tumour markers.
Endpoints/primary	Ovarian cancer mortality at 7 years after randomisation.
outcomes:	To always and the second secon
Inclusion/Exclusion criteria:	Inclusion criteria 1. Age 50-74 years:
criteria:	2. Postmenopausal: Either (a) >12 months amenorrhoea following a natural menopause
	or hysterectomy, or (b) $>12$ months of hormone replacement therapy (HRT) commenced
	for menopausal symptoms.
	Exclusion criteria
	(1) History of bilateral oophorectomy.
	(2) Currently active non-ovarian malignancy. Women who have a past history of
	malignancy will only be eligible if (a) they have no documented persistent or recurrent
	disease and (b) have not received treatment for >12 months.
	(3) Women who have had an ovarian malignancy in the past.
	(4) Women at high risk of ovarian cancer due to familial predisposition as defined by the
	eligibility criteria for the UKCCCR Familial Ovarian Cancer Screening Study.
	(5) Women participating in other ovarian cancer screening trials
Recruitment	Women aged 50-74 will be sent invitations to participate from Heath Authority age/sex
	registers over a 3 year period. Note that women cannot volunteer or be referred to
DI 1 1 1	participate in this trial
Planned sample size:	200,000 postmenopausal women, 100,000 randomised to the control arm, 50,000
Fallers	randomised to multimodal screening, 50,000 randomised to ultrasound screening.
Follow up:	1. Postal questionnaire: All study participants will be asked to complete a health questionnaire midway through the trial and at the end of their participation in the trial
	(i.e. at 3.5 and 7 years after randomisation).
	2. National Health Service Central Register: All study participants will be flagged using
	their NHS number through either the National Health Service Central Register for
	England and Wales or the Cancer Registry of Scotland depending upon their place of
	residence.
Trial duration:	January 2001 - December 2010
Contact details:	UKCTOCS Co-ordinating Centre
	Gynaecological Cancer Research Unit
	Institute of Women's Health, UCL
	[name]
	[name] [contact], [contact]
	http://www.ukctocs.org.uk
L	http://www.aketoes.org.tuk

## United Kingdom Collaborative Trial of Ovarian Cancer Screening (UKCTOCS)

Please complete this form in BLACK INK and in BLOCK CAPITALS. It will help us check that you are eligible for the study as well as collect some data regarding your risk of developing ovarian cancer. If the personal or GP details are incorrect please insert the correct details into the "Amended details" box.

Y	our Personal Details		Amer	ded	deta	ails							
	our GP Details												
Di													
NI	HS No. D.o.B.		AP						ID				
Yo	our Home Telephone No.												
V	Nur Work Tolonbono No										1	 	
YC	our Work Telephone No.												
E	LIGIBILITY DETAILS (use black ink a	and BLOCK	CAPITA	ALS c	r pla	ce a	cros	ss "X	" in th	ne ap	propri	ate bo	xes)
1.	When was your last period? (dd/i	mm/yyyy)				/ [			/				
2.	Are you currently on Hormone Re	placemer	nt The	rapy	/ (H	RT)	?	Ye	s	]		No	
	If Yes then when did you start to (de	aking HR  d/mm/yyy				/ [			/				
3.	Have you had both your ovaries r	emoved?						Ye	s			No	
4.	Have you ever had cancer diagno	sed (exce	ept sk	in ca	ance	er)?		Ye	s	]		No	
	If yes, what cancer was it?											Go to	Q5
	Ovary Breast	Bow	el		Lu	ng			Oth	er			
	When was it diagnosed? (dd/m	ım/yyyy)				/ [			/				
5.	Have you had any treatment for a surgery, chemotherapy, radiother months(not including tamoxifen)?	apy) in the	•		g	_		Ye	s	]		No	

 
6. If any of the following relatives have had OVARIAN CANCER please write the number of affected relatives in the approprate box. Please enter 0 for no affected relatives. (e.g. 0 Mother, 2 Sister, 0 Daughter).  Mother Daughter Sister Aunt GrandMother GrandDaughter
 
7. If any of the following relatives have had BREAST CANCER please write the number
 

of affected relatives in the approprate box. Please enter 0 for no affected relatives.  (e.g. 0 Mother, 2 Sister, 1 Daughter).  Mother Daughter Sister Aunt GrandMother GrandDaughter
8. Are you currently taking part in any other ovarian cancer yes No Screening trial?  If yes what is your study reference number?
ADDITIONAL INFORMATION
ID
9. Your height (cm) Your weight (kg)
Or (in) Or (lb)
10. Country of birth (please place an "X" as appropriate)
England Northern Ireland Scotland Irish Republic Wales Elsewhere
11. Ethnic group, please place an "X" in the appropriate box. (If you are descended from more than one ethnic or racial group, please sellect the group you consider you belong to or choose "Any other ethnic origin")
White Indian Pakistani Chinese Bangladeshi
Black-African Black-Caribbean Black-other Any other ethnic origin
12. At what age did you first have your period?
13. How many pregnancies have you had which ended before they reached 6 months (including miscarriages, ectopic pregnancies)?
14. How many pregnancies have you had which lasted beyond 6 months (including all deliveries - both term and preterm)?
15. Have you ever taken the oral contraceptive pill?  If yes, how many years in total did you take the pill?  Yes No Years
16. Have you ever had a hysterectomy (removal of the womb)?  Yes No
17. Have you had a sterilisation operation (To block your tubes)?  Yes No
18. Have you ever had any treatment for infertility?

# GENERAL HEALTH QUESTIONNAIRE (GHQ-12)

Name:	Date:
Name:	Date:

### Please read this carefully.

We should like to know if you have had any medical complaints and how your health has been in general, over the last few weeks. Please answer ALL the questions simply by underlining the answer which you think most nearly applies to you. Remember that we want to know about the present and recent complaints, not those you have had in the past.

It is important that you try to answer ALL the questions.

Have	you recently				
1.	been able to concentrate on whatever you're doing?	Better than usual	Same as usual	Less than usual	Much less than usual
2.	lost much sleep over worry?	Not at all	No more than usual	Rather more than usual	Much more than usual
3.	felt that you are playing a useful part in things?	More so than usual	Same as usual	Less useful than usual	Much less useful
4.	felt capable of making decisions about things?	More so than usual	Same as usual	Less so than usual	Much less than usual
5.	felt constantly under strain?	Not at all	No more than usual	Rather more than usual	Much more than usual
6.	felt you couldn't overcome your difficulties?	Not at all	No more than usual	Rather more than usual	Much more than usual
7.	been able to enjoy your normal day-to-day activities?	More so than usual	Same as usual	Less so than usual	Much less than usual
8.	been able to face up to your problems?	More so than usual	Same as usual	Less so than usual	Much less able
9.	been feeling unhappy and depressed?	Not at all	No more than usual	Rather more than usual	Much more than usual
10.	been losing confidence in yourself?	Not at all	No more than usual	Rather more than usual	Much more than usual
11.	been thinking of yourself as a worthless person?	Not at all	No more than usual	Rather more than usual	Much more than usual
12.	been feeling reasonably happy, all things considered?	More so than usual	About same as usual	Less so than usual	Much less than usual

## SELF-EVALUATION QUESTIONNAIRE STAI Form Y-2

DIRECTIONS	ALM	40		ALMO
A number of statements which people have used to describe themselves are given below. Read each statement and then circle the appropriate value to the right of the statement to indicate how you generally feel. There are no right or wrong answers. Do not spend too much time on any one statement but give the answer which seems to describe how you generally feel.	ALMOST NEVER	SOMETIMES	OFTEN	ALMOST ALWAYS
21. I feel pleasant	1	2	3	4
22. I feel nervous and restless	1	2	3	4
23. I feel satisfied with myself	1	2	3	4
24. I wish I could be as happy as others seem to be	1	2	3	4
25. I feel like a failure	1	2	3	4
26. I feel rested	1	2	3	4
27. I am "cool, calm and collected"	1	2	3	4
28. I feel that difficulties are piling up so that I cannot overcome them	1	2	3	4
29. I worry too much over something that doesn't really matter	1	2	3	4
30. I am happy	1	2	3	4
31. I have disturbing thoughts	1	2	3	4
32. I lack self-confidence	1	2	3	4
33. I feel secure	1	2	3	4
34. I make decisions easily	1	2	3	4
35. I feel inadequate	1	2	3	4
36. I am content	1	2	3	4
37. Some unimportant thought runs through my mind and bothers me	1	2	3	4
38. I take disappointments so keenly that I can't put them out of my mind	1	2	3	4
39. I am a steady person	1	2	3	4
40. I get in a state of tension and turmoil as I think over my recent concerns and inter	rests1	2	3	4

